#### Caregiver Strain Questionnaire (CSQ):

The Caregiver Strain Questionnaire is a well-validated, reliable 21-item measure of selfreported strain experienced by caregivers and families of youth with emotional problems, with responses on a 5-point Likert scale (0 = Not at all, 4 = very much).

**Clinical Global Impression Scale – Improvement (CGI-I):** The CGI-I will be used as a measure of improvement and contains a 7 point scale as follows: 1 = very much improved, 2 = much improved, 3 = minimally improved, 4 = no change, 5 = minimally worse, 6 = much worse, 7 = very much worse. The CGI-I has been used as a measure in previous clinical psychopharmacology trials and will be completed by the study physician and clinician at each visit based upon clinical observations. It is a clinician rated global measure of improvement that will be completed at baseline, weeks 2 through 8 and at follow-up. It takes about 5 minutes.

**Salivary Oxytocin Levels:** Saliva will be collected by means of an Oragene-Discover collection kit (ORG-500). If able, subjects will spit saliva directly into the collection tube. If the child is unable to spit into the tube, we will use Oragene's OG-AC1 assisted collection swabs to collect saliva from the inside subject's cheeks. Samples will be collected pre-dose and one-hour post-dose at baseline, week 4 and week 8. A salivary sample will also be taken at the follow up visit. It takes approximately 10 minutes to complete.

*Justification for Measurement of Salivary Levels:* We have selected salivary measures of OXT, since Gordon et al [73] demonstrated that salivary OXT levels are directly correlated with brain activity and enhancements in brain function. After administration of IN-OXT, levels of salivary OXT increase markedly and have been shown to remain elevated for up to 7 hours after administration vs. placebo. In fact, low doses (16 IU OXT) did not show weaker effects and tended to elevate the initial salivary OXT compared to higher doses (24 IU). Salivary OXT levels on placebo were highly correlated over time, indicating individual stability of OXT levels. Another study [100], utilized a double-blind placebo-control within-subject design. Ten subjects

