were administered IN- OXT or placebo and salivary OXT was measured ten times over four consecutive hours. IN-OXT increased salivary OXT across the entire period. OXT rose dramatically 15 min after administration (from 6.9 pg/ml at baseline to 1265.4 pg/ml), reached plateau at 45—120 min (range = 131.6 and 105.3 pg/ml), and did not return to baseline by 4 h. The findings from these studies support target engagement in the CNS and refute the idea that salivary elevation results solely from movement of mucus from the nasal cavities back into the mouth.

We believe that plasma OXT levels are of less importance, as central and clinical effects do not reflect plasma PK levels, but that salivary OXT levels may be more closely correlated with CNS effects. We do not expect our one hour post-dose measurements to be affected by IN-OXT residue in the nasal cavity. As stated above, Gordon et al. [73] demonstrated salivary levels of OXT 30 minutes post-dose were strongly correlated with changes in brain activity and van IJzendoorn et al [99] demonstrated that salivary OXT levels peak 1 hour post- dose and a dose of 16 IU was correlated with higher salivary OXT levels than a 24 IU dose. Salivary concentrations are being measured at weeks 4 and 8 to determine if salivary OXT concentrations accumulate over time with chronic treatment of IN-OXT and to determine if the levels correlate with changes in clinical symptoms. We will measure both group and individual differences in salivary OXT concentration in addition to correlating individual salivary OXT concentrations at day 1 and weeks 4 and 8 with changes on the [name] Hyperphagia Questionnaire. We also believe that salivary OXT concentration measurements will induce less discomfort than plasma measurement for the children enrolled in the study. In sum, while levels of salivary oxytocin remain elevated for up to 7 hours, the standard and maximum levels observed in prior studies was observed at the 1 hour post-treatment measurement.

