#### **Detailed Description of Analyses**

**Primary Analyses**: Analyses for Specific Aim (1): To compare IN-OXT vs. placebo with respect to improvement in the hyperphagia severity in children with PWS via improvement in scores on the Hyperphagia Questionnaire-Clinical Trials.

The primary analysis will evaluate the hypothesis that IN-OXT will decrease hyperphagia vs. placebo.

- 1. Response to treatment will be assessed in two ways:
  - a. The effects of IN-OXT on hyperphagia will be analyzed using an intent-totreat approach with the two-sample T-test or Wilcoxon rank sum tests to compare treatment groups at specific visits as well as linear mixed effects models to analyze the repeated measures and changes over time.
  - b. The proportion of responders in each treatment group will also be compared. Response will be defined as a 30% or greater decrease in food-seeking and eating behaviors from baseline on the Hyperphagia Questionnaire-Clinical Trials. Dropouts for clinical reasons will be coded as non- responders. Differences in the proportion of responders in each treatment group will be evaluated using the chi-square test and time to response will be assessed using survival analytic techniques.
  - c. All tests will be two-tailed with an alpha level of 0.05.

**Secondary Analyses:** Analyses for Specific Aims (2) through (8): To compare IN-OXT vs. placebo in children with PWS on change in:(2) Repetitive behaviors via scores on the Repetitive Behavior Scale – Revised (RBS-R) and Montefiore-Einstein Rigidity Scale-Revised (MERS-PWS)(3) Weight and body composition via impedance analysis. (4) Quality of Life Measures on the World Health Organization Quality of Life Scale (WHOQOL)(5) Clinical Global Impression Scale (CGI-I) (6) Salivary Oxytocin Concentration (7) Safety Analyses

IN-OXT and placebo groups will be compared to the above secondary measures will be analyzed using methods similar to those outlined above. Associations between outcome measures at a specific time point will be analyzed with the Spearman rank or Pearson correlation coefficient.

- 1. Secondary Aim (1) Repetitive Behaviors
  - *a.* The effects of treatment on frequency and severity of repetitive behaviors will be assessed by fitting linear mixed effects models to the data on the RBS-R scores. We hypothesize that IN- OXT will significantly reduce repetitive behaviors from baseline to endpoint compared to Placebo.

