  - *b.* The effects of treatment on frequency and severity of repetitive behaviors will be assessed by fitting linear mixed effects models to the data on the MERS-PWS scores. We hypothesize that IN- OXT will significantly reduce repetitive behaviors from baseline to endpoint compared to Placebo.
- 2. Secondary Aim (2) Weight, BMI (z-score) and body composition via bioelectrical impedance analysis
  - a. Weight and BMI (z-score) will be measured at each visit. It will be utilized to evaluate whether IN-OXT significantly modulates energy metabolism and reduces weight compared to placebo. Body composition via impedance analysis will be measured at baseline and endpoint.
- 3. Secondary Aim (3) Quality of Life Measures
  - a. The relationship between quality of life and treatment will be assessed using scores on the WHOQOL. We hypothesize that IN-OXT will improve quality of life from baseline to endpoint as measured by an increase in overall score on the WHOQOL from when compared to placebo.
  - b. The relationship between caregiver strain and treatment will be assessed using scores on the CSQ. We hypothesize that IN-OXT will caregiver strain from baseline to endpoint as measured by an reduction in overall score on the WHOQOL from when compared to placebo.
- 4. Secondary Aim (4) Salivary Oxytocin Levels
  - a. Both group and individual differences in salivary OXT concentration will be measured. Correlations between individual salivary OXT concentrations at day 1 and weeks 4 and 8 as well as correlations between OXT and changes in our primary outcome measure, hyperphagia assessed by the [name] Hyperphagia Questionnaire, will be evaluated using the Spearman rank or Pearson correlation. Additional correlation analysis will be performed on salivary oxytocin levels and secondary outcome measures: RBS-R, WHOQOL and CGI-I. We hypothesize that higher concentrations of salivary oxytocin will be correlated with positive changes on each outcome measure, indicating improvement in symptoms.
- 5. Secondary Aim (5) Safety Analyses
  - a. Rates of specific side effects and other adverse events will be tabulated and compared between treatment groups using the chi-square test. Please see the section labeled "Safety Analyses" for further details on how adverse events will be monitored and rated.

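### Salivary oxytocin is to be correlated with outcome change without regard to arm, so with post-dose samples a treatment effect alone can look like a concentration-response relation

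*Combined protocol and SAP*

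**What the plan says.** The analysis is described under Detailed Description of Analyses, Secondary Aim (4). It opens with concentration itself: "Both group and individual differences in salivary OXT concentration will be measured". The correlations of salivary oxytocin with hyperphagia change then "will be evaluated using the Spearman rank or Pearson correlation". Further correlations are planned with RBS-R, WHOQOL and CGI-I. The hypothesis is directional: "We hypothesize that higher concentrations of salivary oxytocin will be correlated with positive changes on each outcome measure, indicating improvement in symptoms".

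The section Justification for Measurement of Salivary Levels repeats the hyperphagia part: group and individual differences will be measured, "in addition to correlating individual salivary OXT concentrations at day 1 and weeks 4 and 8 with changes on the" hyperphagia questionnaire. The introduction to Secondary Analyses names the same two coefficients in general terms: "Associations between outcome measures at a specific time point will be analyzed with the Spearman rank or Pearson correlation coefficient".

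On what the spray does to saliva, the protocol says that after dosing "levels of salivary OXT increase markedly and have been shown to remain elevated for up to 7 hours after administration vs. placebo". It also cites a ten-subject placebo-controlled study in which "IN-OXT increased salivary OXT across the entire period". In that study the level went from 6.9 pg/ml at baseline to a plateau between 105.3 and 131.6 pg/ml at 45 to 120 minutes. In this trial saliva is taken before and one hour after the dose at baseline, week 4 and week 8, with a further sample at follow-up, from those participants who can provide it.

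**The concern.** Both variables in the correlation can depend on randomised arm. The spray raises post-dose salivary oxytocin, and the primary hypothesis is that it also improves the outcome. A coefficient computed across both arms then picks up the gap between two clusters: active participants with high concentration and more improvement, placebo participants with low concentration and less. It would be positive in the hypothesised direction even if, among participants on the same treatment, concentration had nothing to do with response.

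At stake is the interpretation of a listed secondary aim. A reader would take the result as support for a concentration-response relation when it may only restate the randomised comparison. No multiplicity adjustment is planned, so each of the four correlations would be read at 0.05.

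**Working it through.** **Is arm handled elsewhere?** The covariate adjustment in Summary of Analytic Approach concerns treatment comparisons. The interaction list under Additional Analyses does not include saliva. Measuring group differences in concentration does not bring arm into the correlation. No section supplies an arm term or a within-arm restriction.

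**Inputs from the documents.** 25 per arm, d = 0.8, two-sided 5% (Power Analysis); 1:1 allocation; saliva 6.9 pg/ml before and 105.3 to 131.6 pg/ml after dosing. **Assumption.** The documents give no SD for salivary oxytocin. The arm shift s, in within-arm SDs of log concentration, is therefore varied from 1 to 3.

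**The plan's own figure.** Normal approximation: 0.8 × √(25/2) = 2.83; 2.83 − 1.96 = 0.87; power 80.7%. The noncentral t gives 79.1%. The stated 80% is reproduced. No figure is stated for the saliva correlation.

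**Size of the spray effect.** 105.3/6.9 = 15.3 and 131.6/6.9 = 19.1, or 2.7 to 2.9 natural-log units.

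**Expected pooled correlation with zero association inside each arm.** For two equal arms,

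r = (d·s/4) / √[(1 + d²/4)(1 + s²/4)].

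For d = 0.8 and s = 3: 0.6 / √(1.16 × 3.25) = 0.6 / 1.942 = 0.31.

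**Approximate chance of p < 0.05.** Fisher's z with 50 participants: atanh(0.309) × √47 = 0.319 × 6.86 = 2.19; P(Z > 1.96 − 2.19) = 0.59. Simulation (at least 4,000 trials per setting, no within-arm association) agrees. Ranges show the spread between repeated runs:

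| Per arm | d | s | Expected r | Pooled Spearman, p < 0.05 |
|---|---|---|---|---|
| 25 | 0.8 | 1 | 0.17 | 21–22% |
| 25 | 0.8 | 2 | 0.26 | 49% |
| 25 | 0.8 | 3 | 0.31 | 60–61% |
| 25 | 0.5 | 2 | 0.17 | 23–24% |
| 25 | 0.5 | 3 | 0.20 | 29–30% |
| 25 | 0.3 | 3 | 0.12 | 13–14% |
| 25 | 0 | 3 | 0 | 4–5% |
| 20 | 0.8 | 3 | 0.31 | 51% |
| 15 | 0.8 | 3 | 0.31 | 40–41% |

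Pearson on log concentration gives similar rates (62% at d = 0.8, s = 3). Pearson on untransformed, skewed concentrations gives 30% in that setting. Adjusted for arm, the mean correlation is 0.00 and the test rejects in about 5% of trials in every setting.

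**The case against.** - **The plan does not say that the arms are pooled.** True. Pooling is an inference from bivariate coefficients with no stated restriction. It is the natural reading, and if something else is meant the plan needs to say so.
- **Not every sample is affected.** This stands. The baseline pre-dose sample precedes treatment and cannot depend on arm. The cited elevation lasts up to 7 hours; whether later pre-dose samples fall within that window the documents do not settle. A reader might infer that concentration is little more than a label for arm throughout; that is supported only for post-dose samples. The plan does not say which sample enters the correlation.
- **The percentages are not ordinary false-positive rates.** This also stands. When arm affects both variables the pooled correlation really is non-zero, and the hypothesis as worded is met. The hazard lies in what the correlation is taken to mean.
- **The effect on decisions is limited.** A reader might infer that Phase 3 dose choice would be misled. No section uses this correlation to choose a dose; dosing is addressed by a separate exploratory aim on weight-based dosing. The plan calls the study exploratory, but it does so to justify unadjusted multiple testing, which does not remove confounding by arm.
- **Conditioning on arm has a price.** If salivary level mediates benefit, adjustment discards the randomised contrast and leaves differences between patients that were not randomised. Placebo-arm values reflect the body's own oxytocin, so a common slope mixes two quantities. This argues for reporting the active-arm correlation too, not for leaving arm out.

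**Conclusion.** The concern holds for post-dose samples analysed across both arms. Such a correlation is expected to be non-zero whenever the arms differ in outcome, so it cannot by itself separate a concentration-response relation from a restatement of the treatment comparison.

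Its size depends on the true arm effect and on the assumed saliva shift. With 25 per arm, the test is significant in about 21 to 61% of trials at the design effect of 0.8 (shift 1 to 3 SD), and less often with smaller effects or fewer saliva samples. With no arm effect it stays near 5%. A significant result in one trial is therefore possible or likely, not certain.

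The primary analysis is untouched. This is worth correcting because it bears on a listed secondary aim with a directional hypothesis, and the better analysis uses data already planned.

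**What to change.** In Secondary Aim (4):

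1. Name the sample that enters the correlation: pre-dose, one-hour post-dose, or their difference, and at which visit.
2. Make the main analysis a partial Spearman correlation adjusted for arm, or a regression of outcome change on log salivary oxytocin plus arm.
3. Report the correlation within the IN-OXT arm alongside it.
4. If the pooled correlation is shown, label it descriptive and not evidence of concentration-response.

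Make the matching sentence in Justification for Measurement of Salivary Levels agree.

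**Cost.** A few sentences; no new data, visits or participants. The adjusted analysis keeps everyone who gave saliva, up to 50. The active-arm estimate rests on at most 25 and is imprecise: the critical |r| is 2.069/√(23 + 2.069²) = 0.40, against 0.28 for 50, and power at a true r of 0.3 is only about 31%. The adjusted association compares patients with one another and is not protected by randomisation, so it should be reported as such.

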# SPECIFIC AIMS

**Primary:** To compare IN-OXT vs. placebo on changes on the Hyperphagia Questionnaire-Clinical Trials (HQ-CT) from baseline to week 8 in children with PWS. We hypothesize that IN-OXT will be significantly superior to placebo in improving hyperphagia.

Secondary: To compare the change from baseline to week-8 of IN-OXT vs. placebo on:

- 1. Repetitive Behavior Scale-Revised (RBS-R).
  - We hypothesize that IN-OXT will significantly reduce repetitive behaviors from baseline to endpoint as measured by a reduction of the score on the RBS-R when compared to placebo.
  - We hypothesize that IN-OXT will significantly reduce rigid behaviors from baseline to endpoint as measured by a reduction of the score on the MERS-PWS when compared to placebo.
- 2. Weight, BMI (z-score) and Body composition via bioelectrical impedance analysis
  - We hypothesize that IN-OXT will significantly reduce weight and BMI compared to placebo.
  - We hypothesize that IN-OXT will significantly reduce body fat compared to placebo, as measured by body composition via bioelectrical impedance analysis.
- 3. Quality of Life Measures
  - We hypothesize that IN-OXT will improve quality of life measured by an increase in overall score on the WHOQOL from baseline to endpoint when compared to placebo.
  - We hypothesize that IN-OXT will improve quality of life measured by a reduction in overall score on the CSQ from baseline to endpoint when compared to placebo.
- 4. Salivary Oxytocin Concentration
  - We hypothesize that higher concentrations of salivary oxytocin will be correlated with positive changes on each outcome measure, indicating improvement in symptoms.
- 5. Safety Analyses
  - We hypothesize that IN-OXT will not increase side-effect burden from baseline to endpoint compared to placebo.

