**Research Strategy And Feasibility:** We propose a three year, phase 2, randomized doubleblinded 8-week treatment trial of IN-OXT vs. placebo in 50 child and adolescent subjects (25 male and 25 female) aged 5 to 17 years with a diagnosis of PWS. PWS diagnosis will be confirmed by study team via patient interview and confirmation by patient's past medical records and genetic testing results. At the screening visit, patient will have the opportunity to learn about the study and seek clarification on any outstanding questions. If patient voluntarily agree to participate, study team will work with the patients to complete the informed consent and if applicable, assent. In addition, a psychiatric interview and medical history review will be conducted to screen the patient for eligibility. The study team will also review patient's concomitant medications, assess for patient condition with CGI-S and hyperphagia using the Hyperphagia Questionnaire-Clinical Trials (HQ-CT). If patient meets selection criteria, the study team will arrange on behalf of the patient for an out-patient Quest visit, at which time patient will be asked for a screening blood draw to provide information on CBC, BMP, LFT, IGF-1, thyroid panel, lipid panel, testosterone, estrogen, hemoglobin A1C, and for applicable patient, a urine pregnancy test. Once the screening blood work results are available and all results are within acceptable range, and patient is otherwise eligible, patient will be invited for an in person visit to clinic where additional assessments including a complete physical and neurological exam, intelligence test, interval health or medication change, and if applicable, repeat urine pregnancy test will be conducted. If patient continues to meet all study inclusion and exclusion criteria and agrees to continue with study participation, the study team will formally submit the patient for randomization. The randomization is done in a 1:1 placebo to oxytocin ratio and stratified for gender. The result is blinded to the study team and the process is performed by the study pharmacist at the Clinical Research Pharmacy using a computer generated randomization table. Patients will receive a supply of oxytocin spray bottle with each spray dispensing 4 IU, or a matching placebo. The participant will start with an initial dose of 2 sprays per nostril (4 sprays per day), or 16 IU/day IN-OXT or placebo. To allow for optimization for adverse events or lack of response, we allow for one downward titration to 12 IU (3 sprays per day), and one upward titration to 24 IU (6 sprays per day) at week 2. This will also allow us to examine the relationship between weight based dosing and treatment response. Syntocinon (synthetic intranasal oxytocin) and matched placebo made by Novartis will be used in this protocol. We have an IND for the use of IN-OXT in PWS (IND 121109).

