  - b. The relationship between frequency of suicidal behaviors will be assessed on the ABC-I to evaluate whether IN-OXT vs. placebo is associated with a change in the irritability subscale of the ABC-I which serves as a surrogate for suicidal ideation in this population.

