**Power Analysis: Sample size justification:** The target sample size for this Phase 2 trial is 25 patients per treatment group. The power for the study has been calculated to generate a detectable signal with the sample size of 50 subjects. With this sample size, the study will have 80% power to detect a minimum effect size of d= 0.8 standard deviations in the outcome measures between groups using a two-sample T-test and a two sided Type I error rate of 5%. The study is powered based on a conservative estimate from a heterogeneous population. We expect that in this homogeneous PWS population selected to match study drug to underlying mechanism, the true power will exceed the conservative estimate. This minimum detectable difference is smaller than the treatment effects observed in our previous studies of IN-OXT in adults with ASD, which demonstrated an effect size of d=1.2 on a social cognition measure (RMET) [3], and an effect size of d = 0.84 on a quality of life measure (WHOQOL) [3]. In addition, our previous study of a V1a antagonist in adults with ASD demonstrated an effect size of d=0.8 on a social cognition measure (ASR Lust) [80], and an effect size of d = 0.8 on an Eye Tracking measure (Biological Motion Preference) [90]. The above effect sizes observed in our pilot data were based on a heterogeneous sample of ASD patients characterized by over 100 known different genetic contributing factors. In the proposed trial, both males and females will be included, and any heterogeneity in outcomes due to gender may attenuate overall treatment differences. However, by selecting an orphan population (PWS) with a single unique genetic contribution, and selecting a treatment that matches the known molecular mechanism (IN-OXT), we expect that the treatment effects in this study will nevertheless be greater than the effects observed in earlier studies.

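### The safety hypothesis is one of no increase in side effects, but the only stated test of adverse event rates is a chi-square test of difference, which cannot support it

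*Combined protocol and SAP*

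**What the plan says.** Both Specific Aims sections carry the same secondary safety hypothesis: "We hypothesize that IN-OXT will not increase side-effect burden from baseline to endpoint compared to placebo". Burden is not defined.

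The matching analysis, under Detailed Description of Analyses, Secondary Aim (5), has two parts. For adverse events: "Rates of specific side effects and other adverse events will be tabulated and compared between treatment groups using the chi-square test". For behaviour, the Aberrant Behavior Checklist irritability subscale (ABC-I) is used "to evaluate whether IN-OXT vs. placebo is associated with a change in the irritability subscale of the ABC-I". The Primary Analyses list adds a rule worded to cover everything: "All tests will be two-tailed with an alpha level of 0.05".

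The Safety Analyses section under Assessment of Safety describes tables of treatment-emergent adverse events (TEAEs) by treatment group, with counts, percentages, severity, relatedness, serious events and discontinuations. These are descriptive.

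On size: "The target sample size for this Phase 2 trial is 25 patients per treatment group". The one power statement, in the Power Analysis paragraph, concerns continuous outcomes: "the study will have 80% power to detect a minimum effect size of d= 0.8 standard deviations", by a two-sample t-test at two-sided 5%.

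No section gives a non-inferiority margin, an estimate or interval for the between-arm difference in adverse event rates, an expected adverse event rate, or power for safety. None says how a non-significant chi-square result will be interpreted.

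**The concern.** The hypothesis and the test face in opposite directions. The chi-square test takes equality as its null and looks for evidence against it. A small p-value would count against the hypothesis of no increase. A large p-value leaves it open, because it shows only that the data did not rule out equality. The hypothesis therefore has no route to support under the stated analysis.

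This matters because the participants are aged 5 to 17 and the protocol itself raises a specific harm. It reports more temper tantrums at higher doses in an earlier crossover trial in this syndrome (p = 0.023), and gives that as a reason for using the ABC-I. The trial is also meant to inform Phase 3 and eventual approval, so a loosely worded safety statement would be carried forward. The risk of such wording is realistic. The Risks section takes reassurance from the group's own 6-week work having shown no adverse event difference, and the 6-week study described under Preliminary Study 1 had 19 patients.

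**Working it through.** **Inputs from the documents.** 25 per arm, allocated 1:1; two-sided alpha 0.05; chi-square test for adverse event rates.

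**Assumed inputs.** Placebo event rates of 5% to 40% and increases of 10 to 30 points, because the documents give none.

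**1. The plan's own figure.** For a t-test at d = 0.8, the normal formula is n = 2(1.960 + 0.842)² / 0.8² = 2 × 7.85 / 0.64 = 24.5, so 25 per arm. Exact noncentral-t power at 25 per arm is 79.1%. The stated 80% reproduces, but it does not apply to a comparison of proportions.

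**2. Power of the chi-square test at 25 per arm.** With p̄ the mean of the two rates, the normal approximation is

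power = Φ{ [ |p1 − p0| − 1.96 √(2p̄(1 − p̄)/25) ] / √[ (p0(1 − p0) + p1(1 − p1))/25 ] }.

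For 10% versus 30%: (0.200 − 1.96 × 0.1131) / 0.1095 = −0.199, giving 42%. For 20% versus 40%: (0.200 − 1.96 × 0.1296) / 0.1265 = −0.427, giving 33%. For 10% versus 20%: (0.100 − 1.96 × 0.1010) / 0.1000 = −0.980, giving 16%.

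Exact power, from summing binomial probabilities over all 26 × 26 tables:

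| True rates (assumed) | Approximation | Exact, uncorrected | Exact, continuity-corrected |
|---|---|---|---|
| 10% vs 30% | 42% | 45% | 27% |
| 20% vs 40% | 33% | 35% | 23% |
| 10% vs 20% | 16% | 17% | 6% |
| 20% vs 30% | 12.5% | 13.5% | 6% |

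For 80% power on the approximation, the true increase must be about 32 points from a 5% placebo rate, 35 from 10%, 38 from 20% and 39 from 30%.

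**3. What a non-significant result leaves open.** The intervals are Newcombe hybrid-score 95% intervals for oxytocin minus placebo.

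- 3/25 in each arm: each Wilson interval is 0.042 to 0.300. The half-width is √[(0.120 − 0.042)² + (0.300 − 0.120)²] = 0.196, so the interval is −20 to +20 points.
- 7/25 versus 3/25: χ² = 50(7 × 22 − 3 × 18)² / (10 × 40 × 25 × 25) = 2.0, p = 0.16, interval −7 to +37 points.
- 11/25 versus 5/25: χ² = 50(11 × 20 − 5 × 14)² / (16 × 34 × 25 × 25) = 3.31, p = 0.069, interval −2 to +46 points.

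**4. Would a margin-based test be feasible?** With equal true rates p, margin m, one-sided 0.025 and 80% power, n = 2p(1 − p) × 7.85 / m². At p = 20% and m = 20 points (both assumed), n = 0.32 × 7.85 / 0.04 = 62.8, so 63 per arm. With 25 per arm the power of that test is 42%. Over rates of 10% to 40% and margins of 10 to 20 points it runs from 11% to 65%. A formal test of no increase is not realistic at this size.

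**5. The ABC-I.** An unadjusted comparison of means at 25 per arm has a 95% interval of about ± 2.01 × √(2/25) = ± 0.57 standard deviations. That is more informative than a count of events, but the plan does not commit to reporting it.

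**The case against.** The strongest reply is that the plan never says a non-significant chi-square will confirm the hypothesis. It says that rates will be tabulated and compared, and the hypothesis reads as an expectation. This stands. A reader might infer that p > 0.05 is the plan's criterion for no increase, and that a rise from 10% to 30% would therefore be declared absent 55% of the time. The documents do not support that. The 55% (100% − 45%) is the probability of a non-significant test under assumed rates, not of a wrong conclusion.

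Safety also does not rest on this test alone. TEAEs are tabulated by arm, so a reader could derive an interval from the counts. A safety monitor reviews at least monthly, a medical monitor reviews after each visit, and the data safety monitoring committee may see unblinded data and recommend stopping. Temper outbursts are also covered by the ABC-I, a continuous score collected at each visit from baseline. Secondary measures are to be analysed by methods like those for the primary outcome, which include mixed models that yield an effect estimate. All of this reduces the concern. It does not give a stated interval for the adverse event difference, and oversight during the trial does not govern the final between-arm conclusion.

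The trial is Phase 2 and its outcome analyses are called exploratory; low power for adverse events is usual with 50 patients. That is fair, but it argues for estimation rather than for relying on a difference test. Finally, the chi-square is applied event by event without multiplicity adjustment, so chance positives are possible too. An interval helps to read either kind of result.

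**Conclusion.** The point holds in a limited form. The safety hypothesis is one of no increase. The only stated between-arm analysis of adverse event rates is a two-sided test of difference, without margin, estimate or interval, and that analysis cannot support the hypothesis. The plan is silent on how non-significance will be read. If it were read as no increase, the evidence would be weak: a doubling from 20% to 40% would give a non-significant result about two times in three, and equal counts of 3/25 would still leave an excess of about 20 points inside the interval.

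The event rates are assumptions. The conclusion does not depend on a particular choice, since 80% power needs a true increase of about 32 to 39 points across placebo rates of 5% to 30%. It would be going too far to say that the plan commits the trial to an unsupported safety claim, or that the harm of most interest goes unassessed. The effect is confined to what the trial can say about safety; the primary efficacy result is untouched.

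**What to change.** In Secondary Aim (5):

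1. Add the between-arm risk difference with a 95% confidence interval (for example Newcombe) for patients with any TEAE, with any related TEAE, and with aggression or temper-tantrum events. Fix the list of terms for the last group before unblinding.
2. Report the ABC-I mean difference between arms with its 95% confidence interval.
3. Restate the aim, here and in both Specific Aims sections, as estimating the difference in side-effect burden.
4. State that a non-significant chi-square will not be reported as evidence of no increase, and that the safety conclusion will describe the size of increase the interval does not exclude.

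No margin is proposed, because a margin-based test is not feasible at 25 per arm. The chi-square comparisons can stay as a descriptive screen.

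The cost is some wording and one added column in the adverse event table, using data already collected. The safety statement will be less favourable than a bare report of no significant difference, but it will be supportable.
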